## 1. Purpose of the Study and Background

The proposed study involves developing and testing a computer-assisted approach to delivery of screening and brief interventions, using a 'Substance Use Screening and Intervention Tool (SUSIT)' in primary care patients. Our central hypothesis is that introducing the SUSIT will facilitate the integration of substance use screening and interventions into primary medical care, resulting in higher rates of brief intervention by primary care providers and lower rates of unhealthy drug use in patients who receive the SUSIT intervention, as opposed to screening only. We propose to develop clinical decision support (CDS) and then test the full SUSIT model, incorporated into primary care medical visits. A mixed methods approach will assess its acceptability and adoption among providers and patients, and gather preliminary data on its efficacy for reducing 'moderate-risk' drug use (defined as unhealthy use that is below the threshold of a substance use disorder). In the main study period, a pre-post design will ascertain the dose of substance use intervention received and changes in drug use among patients with moderate-risk drug use enrolled in the screening only (SO) versus SUSIT intervention period (n=75 in each period).

### 1.1. Specific aims

This study has 3 specific aims:

Aim 1 is to develop clinical decision support that assists primary care providers in carrying out a brief intervention.

Aim 2 is to assess the impact of the SUSIT on dose of substance use brief intervention received by patients.

Aim 3 is to gather preliminary evidence on the efficacy of the SUSIT approach for reducing moderate-risk drug use.

### 1.2. Background

Substance use accounts for more morbidity, mortality, and disability than any other preventable condition. While the vast majority of unhealthy substance use is not severe enough to rise to the threshold of a substance use disorder, it nonetheless confers a significant burden of health risk. Individuals with 'moderate-risk' use, who use drugs or alcohol at hazardous levels but have not developed dependence or severe problems related to use, are at elevated risk for developing a substance use disorder and for experiencing negative health effects including overdose death, traumatic injury, direct health effects of substance use, and poor treatment of other medical conditions. These individuals rarely receive assistance, because substance use is not addressed in general health care settings, and addiction treatment programs serve only those with more severe disorders. Screening, brief intervention, and referral to treatment (SBIRT) programs have been advanced as a strategy for addressing the gap in services for early identification and intervention, but these programs have been difficult to implement and sustain, and have not proven efficacious for reducing drug use.

There is an urgent need to examine new models of care that could effectively address unhealthy drug use in primary care settings. SBIRT studies have tested a 'specialist' model, which shifts the responsibility for screening and interventions onto a specialized health educator who is not part of the regular primary care team. An alternative model, which integrates screening and interventions into regular primary care, using the same approaches that are effective for other common chronic health conditions, may be more effective for reducing unhealthy drug use. Innovative application of health information technology can overcome barriers to implementing a primary care-integrated approach.

The significance of our proposal is that it develops and tests an alternative model that fully integrates screening and interventions for unhealthy drug use into regular primary care services. By taking full

advantage of the existing therapeutic relationship and clinical interactions between the patient and their PCP, a primary care-integrated approach should have greater efficacy for reducing unhealthy drug use. Research on behavioral health treatment in primary care has clearly established that primary care provider involvement is a key component of effective interventions. Studies on alcohol and tobacco interventions show that PCP-provided counseling is more effective than that delivered by other care providers. The PCP is at the center of evidence-based approaches to chronic disease management in primary care, including collaborative care models for treatment of depression. The importance of the PCP-patient relationship appears to hold true for drug interventions as well; preliminary results from a study testing a model in which PCPs participated in the brief intervention demonstrated reduced drug use at 3 months.

A primary care-integrated approach to addressing unhealthy drug use has not been adopted due to implementation barriers, the most prominent of which are the time and knowledge required to screen, conduct a clinical assessment, and deliver a brief intervention during the medical visit. Innovative application of existing health information technology can overcome these barriers. The three elements of our Substance Use Screening and Intervention Tool (SUSIT) are designed to facilitate a primary care-integrated approach to substance use intervention. 1) Time and workflow constraints are addressed with patient self-administered screening completed before the clinical encounter, with results presented to the primary care provider at the point of care. 2) Clinical decision support (CDS) assists the primary care provider in carrying out a brief intervention, while 3) clinical reminders at each follow-up visit prompt PCPs to address drug use in a longitudinal fashion. These features facilitate implementation and support effective clinical intervention in the context of the medical visit.

**Substance Use Screening and Intervention Tool (SUSIT)**

1. Self-administered screening
2. Clinical decision support
3. Clinical reminders

The SUSIT screener consists of the Substance Use Brief Screen (SUBS), followed by the ACASI ASSIST. [name] K23 research established the SUBS and ACASI ASSIST as reliable and accurate self-administered screening tools that are brief enough for use in primary care settings, and well accepted by patients. The 4-item SUBS identifies past-year unhealthy use of tobacco, alcohol, illicit drugs, and non-medical use of prescription drugs. The SUBS was validated in 586 adult patients from two urban safety-net primary care clinics, and demonstrated good sensitivity and specificity for detection of past year unhealthy use of tobacco (sensitivity 98%, specificity 96%, AUC 0.97); alcohol (sensitivity 85%, specificity 77%, AUC 0.81); and drugs (sensitivity 83%, specificity 91%, AUC 0.87 for illicit or prescription drug use). The ACASI ASSIST was modified from the WHO Alcohol, Smoking and Substance Involvement Screening Test (ASSIST) to integrate items on prescription drug misuse (stimulants, opioids) and to be delivered as an audio computer-assisted self-interview (ACASI). In the TEST screening approach, the ACASI ASSIST functions as a brief structured assessment that flows seamlessly from the SUBS, to collect substance-specific information about what drugs are used and risk level (low, moderate, high). In the validation study (N=393), ACASI ASSIST scores were highly correlated with those from the reference standard interviewer-administered ASSIST (ICC=0.94 for global ASSIST score). The ACASI ASSIST was feasible even in a study population with relatively low levels of education: 5% required assistance, and median completion time was 3.7 minutes (range 0.7-15.4). Qualitative interviews and surveys indicated that the ACASI ASSIST was well accepted by patients: 27% preferred the computer over an interviewer, while 58% had no preference.

### 1.3. Study design

The proposed study will develop (in Phase 1) a clinical decision support tool that assists primary care providers in carrying out substance use interventions, and then compare (in Phase 2) two

PROTOCOL

s16-01074

[figure not shown]
clinical scenarios, screening only (SO) vs. SUSIT, on dose of substance use brief intervention

Version 8.6

01/22/2019

received, and changes in drug use at 3 and 6 months, among primary care patients. We will develop the CDS component and then test the full SUSIT approach, using mixed methods to assess its acceptability and adoption, and gathering preliminary data on its efficacy for reducing unhealthy drug use. CDS development is concurrent with the SO phase to avoid losing valuable time, but will be conducted at a secondary study site to avoid contaminating the SO condition. In each treatment condition we will enroll 75 patients with moderate-risk drug use, who present for a medical visit with one of ten PCPs (Figure 1). A pre-post design will ascertain the dose of substance use intervention received and changes in drug use among patients enrolled in the screening only (SO) versus SUSIT intervention period.

Figure 1: Study design

## **2. Characteristics of the research population**

Main study sites: Bellevue Hospital Center (BHC) and Gouverneur Health will serve as the main study sites. Both sites serve a diverse and medically underserved population. The proposed study will recruit patients and primary care providers (PCPs) from the adult primary care clinics and the virology clinic at Bellevue Hospital Center. Up to 265 participants will be enrolled in the study. In Phase 1, up to 50 patients from Gouverneur Health and 35 PCPs from Bellevue and Gouverneur will participate in CDS development. In Phase 2, 150 patients and up to 30 PCPs from all study sites will participate.

Enrollment only sites: Two additional clinics are enrollment only sites, with limited study activities, in Phase 2 only. The enrollment only sites are two HIV clinics that function as primary care clinics. These sites are located at Lincoln Hospital in the Bronx, and Kings County Hospital in Brooklyn. Including these sites in the study offers an opportunity to understand the feasibility and impact of the SUSIT approach in a larger and more geographically diverse population of HIV primary care patients, but does not change the overall study aims or design. Enrollment only sites will have the same inclusion and exclusion criteria. The patients and PCPs from these sites are included in the overall limit (maximum 150 patients and 30 PCPs in Phase 2) for enrollment across all study sites.

### **2.1. Demographic characteristics**

Race/Ethnicity and Gender: We anticipate that study participants will reflect the gender and racial characteristics of the participating clinic(s). Forty-five percent of Bellevue patients are of Hispanic ethnicity (representing many countries), 40% are African American (including Caribbean and African immigrants), and 10% are Asian American. No one will be excluded from participation on the basis of gender, race, or ethnicity.

Age: Study participants will be adults 18 years of age and older.

## **2.2. Inclusion and exclusion criteria**

Primary Care Providers: Up to 65 PCPs are anticipated to participate in the study. In Phase 1, up to 35 PCPs from Gouverneur Health and Bellevue will participate in content development, usability testing and clinical testing of the clinical decision support tool. In Phase 2, up to 30 PCPs from Bellevue Hospital will participate. Participating PCPs can be medical doctors (MDs), doctors of osteopathic medicine (DOs), nurse practitioners (NPs), or physician assistants (PAs). Medical students and residents are not included. There are no additional eligibility or exclusion criteria for providers.

**Patients:** Up to 200 patients are anticipated to participate (50 in Phase 1, and 150 in Phase 2). Patients are recruited if they have a medical visit with one of the participating PCPs. Because the SUSIT self-administered screening instrument is currently available in English and Spanish, the study is restricted to English and Spanish speaking patients.

Inclusion criteria:

- Substance use screening results (collected using the tablet-based screening tool) indicating current moderate risk drug use, based on a substance specific involvement score (SSIS) indicating current (past 3 months) use of at least one drug with a moderate risk level (SSIS 4-26), in the absence of any high-risk drug or alcohol use (SSIS 27+);
- 18 years or older;
- English and Spanish speaking;
- Presenting for visit with a participating PCP; and
- Able to provide informed consent
- Available to complete two follow up visits (3 months and 6 months after baseline appointment)

Exclusion criteria:

- Prior participation in the study (i.e. participation in the SO study phase would preclude participation in the SUSIT phase);
- Attending a formal addiction treatment program (not including informal treatment such as Alcoholics Anonymous, Narcotics Anonymous), in the past 3 months;
- Pregnant (based on self-report).
- Unable to read text on the tablet-based screening tool, or physically unable to operate the tablet.

The PI's prior study in this clinic indicates that 17% of all patients will meet eligibility criteria.

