**SUSIT condition:** Following completion of substance use screening, the tablet computer presents screening results (including level of risk) to the patient for each substance used, asks them to identify their drug of most concern (DOMC), and assesses readiness and confidence to change behavior. Results are delivered to the PCP at the point of care, paired with clinical decision support tailored to the patient's screening results. This information is delivered on the tablet computer, which is handed to the PCP by a Medical Assistant. CDS guides the PCP through a brief intervention specific to the DOMC, recommends clinical actions pertaining to the substance and risk level, and generates a printed summary for the patient. At each scheduled follow-up medical visit, the PCP receives a clinical reminder containing a summary of the patient's substance use and level of risk, paired with CDS that guides them through a follow-up brief intervention. A member of the study team will call, email, or text patients prior to these scheduled follow-up medical visits, to confirm that they will be attending.

**Phase 2 SUSIT Condition at Enrollment Only Sites:** Enrollment only sites will participate only in the Phase 2 SUSIT condition. All research activity at these sites is conducted by NYU Research Staff. The NYU research staff will obtain consent and enroll study participants (including both PCPs and patients), and only those individuals who give consent for participation will have any involvement with the study at these sites. After obtaining consent, the NYU research staff will conduct assessments

with enrolled patients at the baseline, 3 month, and 6 month study visits.

Patient participant assessments in SO and SUSIT conditions (Table 1)

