#### Quantitative data analysis (Phase 2):

The data structure follows a hierarchy of patient-level data nested within providers, during the SO vs. SUSIT study period. For analysis of the primary outcome, which is measured at the patient level, we will first examine whether any brief intervention occurred, in at least one visit, during the study period. For additional descriptive information we will count the number of visits in which an intervention occurred, and the number of elements of the brief negotiated interview documented in each visit. The “receipt of brief intervention” outcome analyses will use a generalized linear mixed model (i.e., multilevel logistic regression) with a random intercept and patients nested within primary care providers. The key explanatory variable will be treatment condition (SUSIT vs. SO). When the fixed effect of treatment condition is exponentiated, this coefficient indicates how the odds of receiving brief intervention are multiplied when an individual receives the SUSIT condition rather than screening only. Patient-level and PCP-level covariates (e.g., substances used, provider SAAS score) can be added to the multilevel logistic regression analysis if they are significantly related to the odds of intervention. Any patient-level covariates will be grand mean centered following our focus on treatment condition effects.

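### The Phase 2 provider count and sites are inconsistent, and the primary model has no within-provider check although some providers will contribute to the SUSIT period only

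*Combined protocol and SAP*

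**What the plan says.** - **Entry rule for providers.** Section 2.2 lists eligible professions, leaves out students and residents, and closes with "There are no additional eligibility or exclusion criteria for providers". A patient qualifies by presenting to a participating PCP.
- **Number and sites.** Section 1.3 describes 75 patients per condition "who present for a medical visit with one of ten PCPs". Section 2 says "In Phase 2, 150 patients and up to 30 PCPs from all study sites will participate". Section 2.2 says "In Phase 2, up to 30 PCPs from Bellevue Hospital will participate".
- **One-period sites.** Section 3.1.b states that "Enrollment only sites will participate only in the Phase 2 SUSIT condition". Section 2 counts the PCPs and patients of these two HIV clinics within the Phase 2 maximum of 30 PCPs and 150 patients.
- **Analysis.** Section 3.2.a plans a multilevel logistic model for receipt of brief intervention "with a random intercept and patients nested within primary care providers", with condition as the key explanatory variable. Patient-level and PCP-level covariates, for example the provider attitude score (SAAS), may enter if they are significantly related to the outcome. The section has no within-PCP term, no rule for PCPs seen in one period only, and no supportive analysis by overlap.

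**The concern.** Condition is set by calendar period, so much of the design's strength lies in observing the same PCPs before and after SUSIT begins. A PCP with patients in one period only carries no within-PCP information on SUSIT.

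A random-intercept model does not discard such PCPs. It assumes that PCP propensity is unrelated to condition and uses them as between-PCP evidence. If SUSIT-only PCPs differ on average in how readily they deliver brief intervention, part of that difference is reported as a SUSIT effect. The intercept shrinks the error but does not remove it.

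The protocol itself says, when introducing the SAAS in the Phase 2 PCP assessments, that provider attitudes can influence delivery. The odds ratio at risk is the one for the primary outcome.

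**Working it through.** **1. Which PCP count fits the plan's own total?** Section 2 gives up to 265 participants: 50 Phase 1 patients, 35 Phase 1 PCPs, 150 Phase 2 patients and 30 Phase 2 PCPs.

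- With 30: 50 + 35 + 150 + 30 = 265, which reproduces the stated total.
- With 10: 50 + 35 + 150 + 10 = 245.

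So 30 is the ceiling the total was built on, while ten still stands in the design section. The average load is 150/10 = 15 patients per PCP, or 150/30 = 5. The plan gives no power calculation, intraclass correlation (ICC) or expected rate of intervention, so everything below rests on assumed values.

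**2. How much of a PCP difference passes through a random intercept?** Take a linear random-intercept model with total variance 1 and ICC ρ. For a PCP with n patients, s of them under SUSIT, let k = ρ/(1 − ρ + nρ). Then:

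- A11 = Σ(n − kn²), A12 = Σ(s − kns), A22 = Σ(s − ks²), summed over all PCPs;
- B = Σ(n − kn²), summed over SUSIT-only PCPs;
- leakage L = B(A11 − A12)/(A11·A22 − A12²).

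L is the share of the mean propensity difference that appears as a condition effect.

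Worked case, ρ = 0.10: five PCPs with 8 SO and 5 SUSIT patients, five with 7 and 5, and five SUSIT-only with 5 each (75 patients per condition).

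- A11 = 68.38, A12 = 37.01, A22 = 54.44, B = 16.07.
- L = 16.07 × (68.38 − 37.01)/(68.38 × 54.44 − 37.01²) = 0.21.

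At ρ = 0, L is simply the share of SUSIT patients seen by SUSIT-only PCPs: 25/75 = 0.33 here, and 50/75 = 0.67 with twenty such PCPs.

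| PCPs | ICC 0 | 0.05 | 0.10 | 0.20 |
|---|---|---|---|---|
| 10 in both periods, balanced | 0.00 | 0.00 | 0.00 | 0.00 |
| 10 in both + 5 SUSIT-only | 0.33 | 0.26 | 0.21 | 0.15 |
| 10 in both + 20 SUSIT-only | 0.67 | 0.59 | 0.52 | 0.41 |

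**3. Effect on the planned odds ratio.** This was simulated with the planned logistic model: 75 patients per condition, ten two-period PCPs plus ten SUSIT-only PCPs, intercept −0.7, PCP SD 0.8 logits, true OR 1. There were two separate runs, of 400 and 300 trials per case.

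| Propensity shift (logits) | Mean OR, run 1 | Mean OR, run 2 |
|---|---|---|
| 0 | 0.99 | 1.00 |
| 0.5 | 1.18 | 1.21 |
| 0.8 | 1.31 | 1.34 |

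At a shift of 0.8 the planned test rejected in about 11% of null trials, against 6-7% with no shift.

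**4. Does a within-PCP analysis remove it, and at what price?** With ten SUSIT-only PCPs, refitting in two-period PCPs gave mean ORs of 0.97-0.99. Adding each PCP's proportion of patients enrolled under SUSIT gave 0.94-1.02 across all cases run, with ten or twenty SUSIT-only PCPs.

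The variability of the log OR rose as follows:

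- ten SUSIT-only PCPs: 0.41 to 0.48 with restriction (0.48/0.41 = 1.17), and 0.40 to 0.46 with the added term (1.15);
- twenty: 0.43 to 0.55 (1.28), and 0.43 to 0.57 (1.33).

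**The case against.** **The text points to one PCP cohort.** All participating PCPs are invited to focus groups before SO and again during SUSIT, the SAAS is given twice, and section 5.4 lists a single Phase 2 PCP consent where patients have separate SO and SUSIT forms. This stands as intent. A reader might infer from the open entry rule that Bellevue PCPs did join late or leave between periods. The documents allow that but nowhere say it. The PCP recruitment paragraph in section 5.1 also breaks off in the text available, and Figures 1 and 3 are not shown, so silence there proves nothing. The point rests instead on the enrollment-only sites, where SUSIT-only PCPs are part of the plan.

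**"Up to 30" is a ceiling.** Correct. Ten and up to 30 need not be a strict numerical contradiction. The difference between all sites and Bellevue remains, as does the unexplained ten.

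**Larger biases should not be quoted for Bellevue.** With twenty SUSIT-only PCPs the simulated mean ORs reach about 1.3 to 1.5. If all twenty were at Bellevue, no PCP places would remain for the two HIV clinics, so those figures cannot describe Bellevue turnover.

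**The within-PCP estimate is not clearly better.** With ten SUSIT-only PCPs, the root mean squared error of the log OR at a 0.5 shift is √((ln 1.18)² + 0.41²) = 0.44 for the planned model, against about 0.48 for the restricted fit. At 0.8 it is √((ln 1.31)² + 0.41²) = 0.49 against 0.48. This is a trade of bias against variance. It supports a sensitivity analysis, not a replacement of the primary model.

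**The SAAS score could absorb attitude differences.** Only in part: it enters only if significant, and it would not capture differences between clinics.

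**Conclusion.** The concern holds in limited form. The PCP count and sites need reconciling, and the planned model has no check that separates within-PCP from between-PCP evidence, although some PCPs will certainly be SUSIT-only.

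If those PCPs differ in propensity, the primary odds ratio is shifted. With ten SUSIT-only PCPs who are 0.5 to 0.8 logits higher, a PCP SD of 0.8 logits and no true effect, its mean is about 1.1 to 1.3. With no difference in propensity there is no material bias. The direction is also unknown: less inclined PCPs would pull the estimate the other way.

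A reader might conclude that the planned odds ratio is biased by a known amount. The documents do not support that, because they give neither the number of one-period PCPs nor their difference. A within-PCP estimate would still compare two calendar periods, so it addresses PCP mix and nothing more.

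**What to change.** 1. **Reconcile** sections 1.3, 2 and 2.2 on how many PCPs take part in Phase 2 and from which sites, and state which are expected in both periods.
2. **In section 3.2.a, prespecify one within-PCP sensitivity analysis of the primary outcome.** Either add to the mixed model each PCP's proportion of patients enrolled under SUSIT, or refit in PCPs with at least one patient in each condition.
3. **Report** the number of PCPs and patients by overlap group (SO only, both, SUSIT only), and show the enrollment-only sites separately.
4. **State the reading rule in advance.** The planned odds ratio is interpreted as a SUSIT effect only if the within-PCP estimate agrees in direction and approximate size. Loss of significance through a wider interval is not by itself disagreement.

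A rule requiring PCPs to enter for both periods is not proposed. Section 5.2 mentions SO participants who have finished all visits, and it provides a revised consent form for SUSIT enrollees, so SO enrolment appears complete.

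**Cost:** protocol wording, one extra fit and one table, using PCP identity and condition already collected. The within-PCP interval is about 10-35% wider and draws little or nothing from the enrollment-only sites, which is why those need separate reporting.
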